9.3.2.3 Multiplicity Adjustment

The key secondary endpoints will be formally tested at an alpha of 0.05 only if the primary endpoint is statistically significant. A hierarchical testing procedure will be used to control the type I error rate for the multiple key secondary endpoints tested at an alpha of 0.05. For a test at any step to be considered statistically significant within the testing hierarchy, it must be statistically significant, and all previous tests (if any) within the hierarchy must be statistically significant at the 0.05 level. The testing order of the key secondary endpoints is as follows:

- Absolute change in SwCl from baseline at Week 4
- Absolute change in CFQ-R respiratory domain score from baseline at Week 4

9.4 Safety Analysis

All safety analyses will be based on data from the TE period for the Treatment Period for all subjects in the corresponding Safety Set for the Treatment Period, unless otherwise specified. Subjects will be analyzed according to the treatment they actually received in the Treatment Period. For subjects receiving study drug from more than one treatment group, the treatment group allocation will be the higher treatment group (VX-445/TEZ/IVA > TEZ/IVA).

The overall safety profile of study drug will be assessed in terms of the following safety and tolerability endpoints:

- Treatment-emergent adverse events (TEAEs)
- Clinical laboratory values
- ECGs
- Vital signs
- Pulse oximetry

Only descriptive analysis of safety will be performed and no statistical testing will be performed. The safety data during the Run-in Period will only be presented in listings, unless otherwise specified.

9.4.1 Adverse Events

For analysis purposes, AEs will be classified as pretreatment AEs, TEAEs during the Run-in Period, TEAEs during the Treatment Period, and post-treatment AEs, defined as follows:

Pretreatment AE: any AE that occurred before the first dose date of study drug (TEZ/IVA) in the Run-in Period

TEAE during the Run-in Period: any AE that worsened (either in severity or seriousness) or that was newly developed at or after the first dose date of study drug (TEZ/IVA) through the end of the TE period for the Run-in Period

TEAE during the Treatment Period: any AE that worsened (either in severity or seriousness) or that was newly developed at or after the first dose date of study drug (TC or placebo+TEZ/IVA) through the end of the TE period for the Treatment Period

Post-treatment AE: any AE that worsened (either in severity or seriousness) or that was newly developed after:

- the TE period for Run-in Period if the subject did not receive treatment in the Treatment Period
- the TE period for the Treatment Period if the subject received treatment in the Treatment Period

For AEs with completely missing or partially missing start dates, if there is no clear evidence that the AEs are pre-treatment or TEAE during the Run-in Period or post-treatment, the AEs will be classified as TEAEs corresponding to the Treatment Period. Unless otherwise specified, TEAE refers to TEAE during the Treatment Period.

Details for imputing missing or partial start dates of adverse events are described in [Appendix E](#).

An overview of all TEAEs by treatment group and overall will be summarized in the following categories:

- Number of TEAEs (total number of TEAEs only)
- Subjects with any TEAEs
- Subjects with TEAEs by strongest relationship
- Subjects with TEAEs by maximum severity
- Subjects with TEAEs leading to study drug discontinuation (discontinuation of any study drugs)
- Subjects with TEAEs leading to study drug interruption (interruption of any study drugs)
- Subjects with Grade 3/4 TEAEs
- Subjects with related TEAEs
- Subjects with serious TEAEs

- Subjects with related serious TEAEs
- Subjects with TEAE leading to death

The following summary tables of TEAEs will be presented by treatment group:

- All TEAEs
- Grade 3/4 TEAEs
- TEAEs by strongest relationship
- TEAEs by maximum severity
- TEAEs leading to treatment discontinuation
- TEAEs leading to treatment interruption
- Related TEAEs
- Serious TEAEs
- Related serious TEAEs
- TEAEs leading to death

Summaries will be presented by MedDRA System Organ Class (SOC) and Preferred Term (PT) using frequency counts and percentages (i.e., number and percentage of subjects with an event). When summarizing the number and percentages of subjects, subjects with multiple occurrences of the same adverse event or a continuing adverse event will be counted once, and only the maximum severity level will be presented in the severity summaries, and the strongest relationship level in the relationship summaries.

Additional summary tables will be presented by treatment group for TEAEs showing number and percentage of subjects

- All TEAEs by PT

All AEs, including pretreatment AEs, TEAEs for all applicable periods, and post-treatment AEs, will be presented in an individual subject data listing based on the All Subjects Set. In addition, separate listings containing individual subject adverse event data for TEAEs leading to treatment discontinuation, TEAEs leading to treatment interruption, Grade 3/4 TEAEs, SAEs and all deaths will be provided separately, with a flag indicating the TEAE status for SAEs and deaths.

In addition, the following tables for the Run-in period will be presented by overall based on the Safety Set for the Run-in period.

- An overview of TEAEs during the Run-in Period
- All TEAEs during the Run-in Period by SOC and PT

9.4.1.1 Subgroup Analysis

An overview of all TEAEs and a summary of TEAEs by SOC and PT for the following subgroups will be provided:

- Age at screening (<18, ≥18 years)

- ppFEV₁ at baseline (<70, ≥70)
- Sex (male, female)
- Geographic region (North America, Europe)

9.4.2 Clinical Laboratory

For the treatment-emergent laboratory assessments, the observed values and change from baseline values of the continuous hematology, coagulation and chemistry results will be summarized in SI units at each visit by treatment group.

The number and percentage of subjects meeting at least 1 threshold analysis criterion event, during the TE period for Treatment Period, will be summarized by treatment group. The threshold analysis criterion shift from baseline will also be summarized for selected laboratory parameters. The threshold analysis criteria are provided in [Appendix F](#).

For selected LFT laboratory test (alanine transaminase [ALT], aspartate transaminase [AST], alkaline phosphatase [ALP], and total bilirubin), a scatter plot of the maximum treatment-emergent value versus the baseline value corresponding to ×ULN (upper limit of normal) will be presented. Further, a scatter plot of the maximum treatment-emergent value of ALT and AST, separately, versus the maximum treatment-emergent value of total bilirubin corresponding to ×ULN will also be presented by treatment group.

Results of urinalysis and positive urine/serum pregnancy test will be listed in individual subject data listings only. For positive serum pregnancy listing, subjects with serum HCG which are abnormally high will be selected.

In addition, a listing containing individual subject hematology, chemistry, and coagulation values will be provided. This listing will include data from both scheduled and unscheduled visits.

9.4.3 Electrocardiogram

For the treatment-emergent ECG measurements, a summary of observed values and change from baseline values will be provided at each visit by treatment group for the following ECG interval measurements (in msec): RR interval, PR interval, QT interval, QTcF interval, QRS duration, and Heart Rate (beats per minute).

The number and percentage of subjects meeting at least 1 threshold analysis criterion during the TE period for the Treatment Period will be summarized by treatment group. The threshold analysis criteria are provided in [Appendix F](#).

In addition, a listing containing individual subject ECG values will be provided. This listing will include data from both scheduled and unscheduled visits.

9.4.4 Vital Signs

For the treatment-emergent vital signs measurements, the observed values and change from baseline values will be summarized at each visit by treatment group. The following vital signs parameters will be summarized: BMI (kg/m²), weight (kg), height (cm), systolic and diastolic blood pressure (mm Hg), body temperature (°C), pulse rate (beats per minute), and respiratory rate (breaths per minute).

The number and percentage of subjects meeting at least 1 threshold analysis criterion during the TE period for the Treatment Period will be summarized by treatment group. The threshold analysis criteria are provided in [Appendix F](#).

In addition, a listing containing individual subject vital signs values will be provided. This listing will include data from both scheduled and unscheduled visits.

9.4.5 Pulse Oximetry

For the treatment-emergent oxygen saturation values by pulse oximetry, a summary of observed values and change from baseline values will be provided at each visit by treatment group.

The number and percentage of subjects with shift changes from baseline (normal/missing and low according to the reference range) to the lowest percent of oxygen saturation during the TE period for the Treatment Period will be summarized by treatment group.

9.4.6 Physical Examination

Abnormal PE findings will be presented as an individual subject data listing only.

9.4.7 Supportive Safety Analysis

9.4.7.1 Adverse Events of Special Interest

For this study, elevated transaminase events and rash events, as determined by MedDRA preferred terms in [Appendix G](#), are considered as adverse events of special interest.

For treatment-emergent elevated transaminase events and rash events, the following categories will be summarized by treatment group:

[figure not shown]
- Subjects with events
- Subjects with events by maximum severity
- Subjects with events leading to treatment discontinuation
- Subjects with events leading to treatment interruption
- Subjects with serious events
- Subjects with related serious events
- Subjects with events leading to death
- Duration of events
- Time-to-onset of first event

In addition, for treatment-emergent rash events, these categories will be summarized for the following subgroups:

- Sex (male, female)
- Female subjects with concomitant hormonal therapy (Yes, No)

9.4.7.2 Hormonal Therapy

The number of subjects who used hormonal therapy concomitantly will be summarized by treatment group based on the Safety Set for the Treatment Period.

10 Interim and DMC Analyses

10.1 Interim Analysis

No formal interim analysis is planned.

10.2 DMC analysis

The DMC's objectives and operational details are defined in a separate document (DMC Charter) which was finalized before the first subject was screened in the study. The DMC's planned safety reviews of study data are outlined in the DMC Charter and DMC Statistical Analysis Plan.

12 LIST OF APPENDICES

Appendix A: Analysis Visit Windows for Safety and Efficacy Assessment

Table 12-1 Analysis Visit Windows for Safety and Efficacy Assessments

Assessment	Visit ¹	Target Study Day	Analysis Visit Window ^{2,3,4} (in study days)
Safety Assessment			
Serum Chemistry Hematology	Day 1 (Baseline)	1	≤1 Pre-dose
	Day 15	15	[1, 22]
	Week 4	29	(22, 43]
	Safety Follow-up	Not applicable	Use nominal visit
Standard 12-lead ECG	Day 1 (Baseline)	1	≤1 Pre-dose
	Day 15 Pre-dose and Postdose	Not applicable	Use nominal visit
	Week 4	29	(22, 43]
	Safety Follow-up	Not applicable	Use nominal visit
Coagulation	Day 1 (Baseline)	1	≤1 Pre-dose
	Week 4	29	[1, 43]
	Safety Follow-up	Not applicable	Use nominal visit
Vital Signs (excluding BMI, Weight, Height and their Z-scores)	Day 1 (Baseline)	1	≤1
	Day 15	15	[1,22]
	Week 4	29	(22, 43]
	Safety Follow-up	Not applicable	Use nominal visit
Efficacy Assessment and Pharmacodynamic Assessment			
Spirometry	Day 1 (Baseline)	1	≤1 Pre-dose
	Day 15	15	(1,22]
	Week 4	29	(22, 43]
	Safety Follow-up	Not applicable	>43
Sweat Chloride	Day 1 (Baseline)	1	≤1 Pre-dose
	Day 15	15	(1,22]
	Week 4	29	(22, 43]
CFQ-R Weight, Height and BMI	Day 1 (Baseline)	1	≤1
	Day 15	15	(1,22]
	Week 4	29	(22, 43]
	Safety Follow-up	Not applicable	>43

Notes:

¹ Visit name for analysis purpose is used to report data in tables and figures.

² The analysis visit windows will be applied using the following rules for both scheduled and unscheduled visits:

- a. If no numerical measurement is available within a visit window, the measurement will be considered missing for the visit.
- b. If there is more than 1 numerical measurement available within a visit window, use the following rules:
 - i. The measurement closest to the target day will be used; or
 - ii. If there are multiple measurements with the same distance from the target day, the latest measurement will be used.

Table 12-1 Analysis Visit Windows for Safety and Efficacy Assessments

Assessment	Visit ¹	Target Study Day	Analysis Visit Window ^{2,3,4} (in study days)

³ For lab, ECG and vital sign measurement collected on the date of first dose of study drug in Treatment Period, if it cannot be determined whether the measurement is before or after the first dose:
 
 Scheduled measurement will be treated as pre-dose observation. Unscheduled measurement will be treated as post-dose observation. 
⁴ For safety assessment, Safety Follow-up analysis visit will be based on nominal Safety Follow-up visit. If a subject doesn't have a nominal Safety Follow-up visit but has an ETT visit with study day >43, then the ETT visit will be mapped into Safety Follow-up analysis visit.
 
Derived Variables:
 
 Age (in years) at first dose date and nominal visit (for demographics, listing and the calculation of [percent] predicted spirometry variables): 
Obtain the age at informed consent (in days) in “yy, mm” format (e.g., 24 years, 6 months) from the Vital Signs (VS) page at the Screening Visit, and add 0.5 month to convert to days.
 
Obtain the informed consent date.
 
Then age (in years) at first dose or nominal visit = [(first dose date or nominal visit date – informed consent date) in days + age at informed consent (in days)]/365.25.
 Age (in months) at nominal visit (for use in calculation of BMI and weight z-score): 
Obtain the age at informed consent (in months) in “yy, mm” format (e.g., 24 years, 6 months) from Vital Signs (VS) page at the Screening Visit.
 
Obtain the informed consent date.
 
Then age (in months) at nominal visit = integer part of {(age at informed consent (in months) + 0.5 + diff(first dose date or nominal visit date, informed consent date) in months)} + 0.5.
 Missing first dose date or last dose date 
If the first dose date is missing, use Day 1 visit date to impute.
 
If the last dose date is missing or partial date is reported, the last dose date will be imputed based on, in descending order priority, the Early Treatment Termination (ETT) visit date, last visit date before the Safety Follow-up, or the last study drug administration date from EX SDTM domain, as appropriate. The imputation algorithm will ensure the imputed last dose date does not exceed the study participation end date.
 Sweat Chloride: 
Non-missing sweat chloride concentrations from the left arm and right arm with assessment end date/time for a given arm up to 30 minutes after first dose time in treatment period will be considered for baseline.
 Electrocardiogram: 
Baseline is defined as the most recent pretreatment measurement before the first dose of study drug in the Treatment Period. If multiple ECG measurements are obtained on the same calendar day during the TE period,
 
 ○ For summary purpose, the calculated average ECG will be used as the ECG value on that day (except for Day 15 visit); ○ For threshold analysis purpose, all reported ECG values will be used. 			

Appendix B: Imputation Rules for Missing Prior/Concomitant Medication Dates

Imputation rules for missing or partial medication start/stop dates are defined below:

1. Missing or partial medication start date:
 - a. If only DAY is missing, use the first day of the month.
 - b. If DAY and Month are both missing, use the first day of the year.
 - c. If DAY, Month and Year are all missing, use a date before the first dose date (in practical, use Jan. 01, 2000 to impute).
2. Missing or partial medication stop date:
 - a. If only DAY is missing, use the last day of the month.
 - b. If DAY and Month are both missing, use the last day of the year.
 - c. If DAY, Month and year are all missing, assign ‘continuing’ status to stop date (in practical, use Dec. 31, 2050 to impute).

In summary, the prior, concomitant, or post categorization of a medication is described below.

Table 12-2 Prior, Concomitant, and Post Categorization of a Medication

Medication Start Date	Medication Stop Date			
	< First Dose Date of Run-in TE Period	≥ First Dose Date and < End Date of Run-in TE Period	≥ First Dose Date and ≤ End Date of Treatment TE Period	> End Date of Treatment TE Period
< First dose date of Run-in TE period	P	PC1	PC1C2	PC1C2A
≥ First dose date and < End date of Run-in TE Period	-	C1	C1C2	C1C2A
≥ First dose date and ≤ End date of Treatment TE Period	-	-	C2	C2A
> End date of Treatment TE Period	-	-	-	A

P: Prior; C1: Concomitant during the Run-in Period; C2: Concomitant during the Treatment Period; A: Post

Imputation rules for missing and/or partial dates of non-pharmacological treatment/procedure will follow the same imputation rule.

Appendix C: Details of GLI Equations for Calculating ppFEV₁

Percent predicted values will be calculated for parameters of FEV₁, [REDACTED] [REDACTED] using the Quanjer GLI-2012 Regression Equations and Lookup Tables.

The regression equations and lookup tables required to implement the Quanjer GLI-2012 predicted values are available in:

Philip H. Quanjer, Sanja Stanojevic, Tim J. Cole, Janet Stocks. Quanjer GLI-2012 Regression Equation and Lookup Tables (Version 7 April 2013). Global Lung Function Initiative. [online] Available at: <http://www.ers-education.org/home/browse-all-content.aspx?idParent=138978> [Accessed Mar 26, 2018].

The instructions and tools on how to implement the Quanjer GLI-2012 equations are:

Philip H. Quanjer, Sanja Stanojevic, Tim J. Cole, Janet Stocks. Implementing GLI-2012 regression equations (Version 19 July 2015). Global Lung Function Initiative. [online] Available at: <http://www.ers-education.org/home/browse-all-content.aspx?idParent=138979> [Accessed Mar 26, 2018].

Sanja Stanojevic. GLI-2012 - SAS Macro (Version 2, 7 April 2013). Global Lung Function Initiative. [online] Available at: <http://www.ers-education.org/home/browse-all-content.aspx?idParent=138988> [Accessed Mar 26, 2018].

Data handling rule for spirometry is as follows:

- Input age with at least 2 decimal place
- Use height at screening regardless if height is collected at other study visits for subjects whose age at informed consent is >21 years. For subjects with age <=21 years, height collected at the respective visit should be used; if the height at the respective visit is not available, the last non-missing record will be used.
- For race, map the CRF reported Black or African American to Black, all other races in CRF (except White) are mapped to 'other'; multiple checks for race in CRF are also mapped to 'other'; white is a reference race in the equations and assumes 0 values for all race coefficients in the GLI equations.

Appendix D: Steps for Multiple Imputation

For the multiple imputation (MI) to be applied to the MMRM model for the primary efficacy endpoint, the following steps will be followed:

Imputation distribution

The imputation distribution for the missing absolute change from baseline in ppFEV₁ at visit t will be a normal distribution. All randomized subjects will be classified into one of three categories based on the following rules:

- Non-missing category: Subjects who have a ppFEV₁ assessment at Week 4 (i.e., subjects who have a non-missing absolute change from baseline in ppFEV₁ at Week 4).
- Missing category 1: Subjects with missing absolute change from baseline in ppFEV₁ at Week 4, who discontinued treatment because of adverse events, noncompliance with study drug, death, or physician decision, or because the subject refused further dosing or required prohibited medication.
- Missing category 2: Subjects who discontinued treatment for any reason not listed in Category 1 and have missing absolute change from baseline in ppFEV₁ at Week 4, or subjects who have completed 4 weeks treatment duration but are missing the absolute change from baseline in ppFEV₁ at visit Week 4

Imputation algorithm

We will use the following algorithm that relates the mean of the missing absolute change from baseline in ppFEV₁ at visit t to the missing categories defined above. The algorithm will be implemented within each treatment group as follows:

- Missing category 1: randomly draw a sample from the normal distribution(μ_{25}, σ^2), where μ_{25} is the 25th percentile of the non-missing absolute changes from baseline in ppFEV₁ at visit t and σ^2 is the sample variance estimated using the non-missing absolute changes at visit t .
- Missing category 2: randomly draw a sample from the normal distribution(μ, σ^2), where μ is the mean of the non-missing absolute changes from baseline in ppFEV₁ at visit t and σ^2 is the sample variance estimated using the non-missing absolute changes at visit t .

Analysis model

The complete MI method is described below:

- Form an “imputed dataset” by imputing missing values at each visit for those subjects who have a missing value at the visit and have all subsequent values missing. The appropriate normal distribution specified in the algorithm above will be used for each such subject, based on their category.
- Repeat this process K ($K=20$) times to form K imputed datasets.
- Fit the same MMRM model to each imputed dataset to estimate the absolute change at Week 4.
- Combine the results from the K imputed datasets using the SAS procedure MIANALYZE to derive the MI estimator.

Let θ be the true treatment difference. Denote by $\tilde{\theta}_k$ the estimate of θ from the k^{th} imputed dataset, and the corresponding estimate of the variance is denoted by V_k . The MI estimator of θ , $\tilde{\theta}_{\text{MI}}$, is the average of the K individual estimates.

The estimated variance of $\tilde{\theta}_{\text{MI}}$ is a combination of the between- and within-imputation variability as follows: $V_{\text{MI}} = W + \left(1 + \frac{1}{K}\right)B$, where $W = \frac{1}{K} \sum_{k=1}^K V_k$ is the within-imputation variability and is $B = \frac{1}{K-1} \sum_{k=1}^K (\tilde{\theta}_k - \tilde{\theta}_{\text{MI}})^2$ is the between-imputation variance. The statistic $T = \frac{\tilde{\theta}_{\text{MI}} - \theta}{\sqrt{V_{\text{MI}}}}$ has an approximate t_V distribution, where $V = (K - 1)\left(1 + \frac{W}{B}\right)^2$.

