### 9.3.2 Study Drug Dose

#### VX-445 Dosage

A VX-445 dose of 200 mg qd was selected for the current study based on an assessment of the benefit-risk profile from the ongoing Phase 2 Study VX16-445-001 (Study 445-001) Parts D and E. In Study 445-001 Part D, a range of VX-445 doses (50 mg qd, 100 mg qd, and 200 mg qd) in

TC with TEZ/IVA were evaluated in subjects with F/MF genotypes. Part E of Study 445-001 evaluated a dose of VX-445 200 mg qd in TC with TEZ/IVA in subjects with F/F genotypes. The TC was generally safe and well tolerated in all VX-445 dose groups, and F/F subjects who received the VX-445 200 mg qd TC demonstrated a clinically meaningful improvement in ppFEV1 (within-group mean [SE] absolute change of 11.0 [1.5] percentage points from baseline [ $P < 0.0001$ ], compared with a mean absolute change of 0.4 [2.8] percentage points in subjects who received the active comparator of TEZ/IVA [ $P = 0.8869$ ]).

The dose-response relationship of VX-445 in TC was assessed for ppFEV1 and SwCl for F/MF patients using population-PK/PD modeling. Results indicate that a dose of 200 mg qd provides meaningful improvement for ppFEV1 and SwCl, while a dose less than 200 mg qd may result in some subjects having suboptimal improvements in CFTR function. These dose-response analyses are applicable to the F/F population, with 2 *F508del* alleles. No differences in the safety profile of VX-445/TEZ/IVA were observed across the doses.

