7.2 Sample Size and Power

The primary efficacy endpoint is the absolute change in ppFEV₁ from baseline at Week 4. The primary null hypothesis to be tested is that the mean absolute change in ppFEV₁ from baseline at Week 4 is the same for the TC and TEZ/IVA treatment groups. The null hypothesis will be tested at a 2-sided significance level of 0.05.

Assuming a within-group SD of 7 percentage points and a 5% dropout rate at Week 4, a sample size of 50 subjects in each treatment group for a total of 100 subjects will have approximately 93% power to detect a difference of 5.0 percentage points for the mean absolute change in ppFEV₁ from baseline at Week 4 between the 2 treatment groups, based on a 2-sided 2-sample *t*-test at a significance level of 0.05 using the [REDACTED].

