9.3.1.4 Sensitivity Analysis

MMRM based on Multiple Imputation (MI)

An underlying assumption of the MMRM method is that data are missing at random. To minimize the amount of missing data, subjects who prematurely discontinue study drug treatment will continue to complete all scheduled study visits for spirometry and other efficacy assessments.

To assess the impact of missing data and the assumption that data are missing at random, a multiple imputation algorithm will be used if at least 10% of the subjects have missing changes in ppFEV₁ at Week 4 in any treatment group. Missing absolute change from baseline in ppFEV₁ assessments will be imputed starting from the first visit with missing values, for which all subsequent visits through Week 4 are also missing. For intermediate missing data, i.e., missing values that fall between two non-missing ones, it is reasonable to assume that they are missing at random and therefore will not be imputed. An MMRM analogous to that for the primary analysis of the primary endpoint will be applied to each imputed dataset and the relevant MI estimators will be reported. Details for the MI steps are presented in [Appendix D](#).

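### The only planned check of missing at random centres Category 1 dropouts on their own arm's 25th percentile, so with balanced Category 1 loss it cannot, on average, test whether TC dropouts lose the TC benefit

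*SAP*

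**What the plan says.** SAP 9.3.1.4 gives the purpose of the multiple imputation: "To assess the impact of missing data and the assumption that data are missing at random". It runs only if 10% or more of either arm lacks a Week 4 change. It is the only such check for the primary endpoint. SAP 9.3.1.3 plans no supportive analysis, and neither document states a control-based, delta-adjusted or tipping-point analysis.

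Appendix D sorts subjects without a Week 4 change into two groups. Category 1 holds those "who discontinued treatment because of adverse events, noncompliance with study drug, death, or physician decision", together with those who declined more doses or came to need a disallowed drug. Category 2 holds the rest. On the reference group the appendix is explicit: "The algorithm will be implemented within each treatment group as follows". Category 1 values come from a normal distribution whose centre "is the 25th percentile of the non-missing absolute changes from baseline in" ppFEV1 at that visit, with that arm's observed variance. Category 2 values are centred on the arm's own mean.

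**The concern.** The departure from missing at random that most threatens a superiority claim is that TC subjects who leave do not keep the TC benefit. A useful sensitivity analysis has to be able to show what happens then. Appendix D lowers dropouts in each arm relative to that arm's own completers, so the gap between arms is carried over to the dropouts. If similar proportions leave each arm for Category 1 reasons, the penalty cancels. If more controls leave, it moves the estimate in favour of TC. The result could then be read as evidence of robustness when the question was never put.

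**Working it through.** **Inputs.**
- SAP 7.2: 50 per arm (100 in all); design difference 5.0; two-sided alpha 0.05. On variability and loss: "Assuming a within-group SD of 7 percentage points and a 5% dropout rate at Week 4".
- Protocol 9.3.2, Phase 2 F/F subjects on TC: "within-group mean [SE] absolute change of 11.0 [1.5] percentage points from baseline". TEZ/IVA: 0.4 (SE 2.8). Neither n nor SD is given.
- Assumption: changes are roughly normal, so the 25th percentile is the mean minus 0.6745 × SD.

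**Plan's own figure.** With 50 × 0.95 = 47.5 per arm, the noncentrality is 5 / (7 × √(2/47.5)) = 3.48. Power is 93.1% by noncentral t and 93.6% by the normal approximation. The stated figure of about 93% is reproduced.

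**Where Category 1 is centred.** The shift is 0.6745 × 7 = 4.72 points below the own-arm mean.

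| Assumed arm mean | Centre at SD 7 | Range for SD 5 to 10 |
|---|---|---|
| TC 11.0 (Phase 2) | +6.28 | +7.6 to +4.3 |
| TC 5.0 (design difference, control 0) | +0.28 | +1.6 to −1.7 |
| TEZ/IVA 0.4 | −4.32 | – |
| TEZ/IVA 0 | −4.72 | – |

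Varying the Phase 2 TC mean by ±1.96 × 1.5 at SD 7 gives +3.3 to +9.2.

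**Effect on the treatment difference.** Let D be the observed-case difference, and pT and pC the Category 1 missing fractions. The imputed TC mean is μT − 0.6745 × pT × SD_T, and control is analogous. Hence

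expected difference = D − 0.6745 × (pT × SD_T − pC × SD_C).

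Category 2 sits at the own-arm mean and adds nothing to the expectation.

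| Category 1 missing, TC / control | SDs, TC / control | Expected shift |
|---|---|---|
| 10% / 10% | 7 / 7 | 0.00 |
| 20% / 20% | 7 / 7 | 0.00 |
| 5% / 10% | 7 / 7 | +0.24 |
| 10% / 0% | 7 / 7 | −0.47 |
| 20% / 0% | 7 / 7 | −0.94 |
| 10% / 10% | 8 / 6 | −0.13 |

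**Comparison with a control-based rule.** If Category 1 subjects in both arms are centred on one control-arm value, the expected difference is (1 − p) × D. For D = 5.0 this is 4.50 at p = 10% and 4.00 at 20%, against 5.00 under the SAP rule. For D = 10.6 (11.0 − 0.4) it is 9.54 and 8.48, against 10.6.

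**Simulation.** This was a simplified version: Week 4 only, no Day 15 data or covariates, K = 20, 600 replicates, all missing subjects in Category 1. The control-based rule was centred on the control 25th percentile. At D = 5 the mean observed and imputed differences were 4.95 and 4.94 with 10% missing per arm, and 4.97 and 4.97 with 20%. The null hypothesis was rejected in about 90% of trials under the SAP rule and 84% under the control-based rule at 10%, and in about 87% and 74% at 20%. At D = 10.6 every trial rejected under both rules.

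**The case against.** Several points on the other side stand.

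- **A reader might infer that a TC dropout is always credited with about +6.** The documents do not support that. The figure combines a Phase 2 mean with the planning SD. At the design difference the centre is about +0.3 with control change 0, or 5.4 − 4.72 = +0.68 with control 0.4. It is also the centre of a random draw with SD 7, not an assigned score.
- **A reader might infer that the rule can never lower the estimate.** It can. With 10% Category 1 loss in TC only it removes 0.47. At D = 5.0, centring those subjects on the control mean would remove 0.10 × 5.0 = 0.50, practically the same. Excess TC loss is a natural pattern if tolerability drives dropout. Even with balanced loss, the cancellation is an average: in single simulated trials the imputed difference fell below the observed one about half the time (SD of the gap 0.17 at 10%, 0.29 at 20%).
- **A reader might infer that Category 1 is the only departure from missing at random.** Category 2 departs too, since it draws from the marginal arm mean and ignores Day 15 and covariates, whereas the primary MMRM conditions on observed data. But it is also an own-arm rule and does not stress the comparison.
- **Exposure is limited.** The trigger is 10% missing against 5% planned dropout. Subjects who stop treatment keep attending visits (Protocol 9.1.5.2, SAP 9.3.1.4), so many off-treatment values will be observed directly.
- **Control-based imputation is not obviously better as a replacement.** Baseline is measured on TEZ/IVA, so placing TC dropouts at the mean of subjects still on TEZ/IVA assumes that level persists after stopping. Leaving control dropouts at their own mean removes any penalty from them. The SAP's −4.3 for a control dropout is closer to losing the 4.0-point TEZ/IVA effect cited in Protocol 9.3.1.

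None of this touches the balanced case. At the design effect a TC dropout is centred near zero, but a control dropout is moved to about −4.7, so the full 5-point gap remains.

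**Conclusion.** The point holds in a bounded form. With equal Category 1 fractions and similar SDs, the planned analysis leaves the expected treatment difference unchanged at any level of missingness, and with more Category 1 loss in control it raises it. The estimate falls only when pT × SD_T exceeds pC × SD_C, that is, through excess TC loss or a larger TC SD. In the balanced case it therefore cannot, on average, test whether TC dropouts lose the TC benefit. At a difference of 5.0, the part left untested is about 0.5 points at 10% and 1.0 point at 20% missing per arm, measured against a control-based rule.

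This rests on approximate normality, the planning SD of 7, and all missing subjects being in Category 1. A reader might go further and infer that the analysis reports robustness by construction, or that the primary conclusion is in danger. The documents do not support either: the analysis does respond to excess TC loss, it runs only above the 10% trigger, and at a Phase 2-sized effect the conclusion held under both rules in the simulation. The gap matters mainly if the effect is nearer the design value and missingness exceeds plan. It is worth closing because it is cheap to close.

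**What to change.** Before database lock, keep the existing imputation and add to SAP 9.3.1.4 and Appendix D, under the same 10% trigger, a tipping-point analysis. Subtract an increasing delta from the imputed TC-arm values only, refit the MMRM, combine as already described, and report the delta at which significance at the two-sided 0.05 level is lost. A control-based imputation of TC Category 1 subjects may be shown as one scenario, with its assumption about the level after stopping stated.

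SAP Section 4 allows amendment before lock. The cost is a paragraph of SAP text, a few lines of code, slightly more analysis work, and a sensitivity result that may look less favourable to TC.
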